2.4 What are the proposed methods for protecting against other sources of bias?

All research and clinical personnel at the study site with the exception of the site pharmacist or responsible team member will be blinded to treatment allocations. Vitamin C is colorless and odorless and a saline or D5W placebo will be used to maintain blinding. Given the nature of our study intervention, it is important that we standardize the practice of nutrition therapy in participating units. As per standard of care in these burn units, these patients will be fed enterally and for those fed into the stomach, they will have routine evaluation of gastric residual volume during feeding. We have considerable experience standardizing feeding practices across ICUs using our national nutrition guidelines, pre-printed orders and bedside algorithms (see tools in www.criticalcarenutrition.com). We provide these tools to all participating centers to harmonize practices between centers and to improve compliance. While we have not standardized the selection of feeding solutions for individual patients, we will provide guidance on using standard equations for the determination of energy and protein intakes. We have also harmonized the use of parenteral nutrition when enteral nutrition fails to meet its goal. All other aspects of burn care will not be standardized but we will capture key process of care issues in our minimalistic data collection strategies.

2.5 What are the planned Inclusion/Exclusion criteria?

Inclusion criteria 18 years of age or older with deep 2nd and/or 3rd degree burns, who are assessed as requiring skin grafting, and a minimum burn size $\geq 20\%$ Total Body Surface Area (TBSA). Patients with smaller burns are less likely to require fluid resuscitation and their risk of morbidity and mortality is lower. Burn size will be determined by the attending physician (and confirmed by the attending surgeon if it is not the same person).

Exclusion criteria

1. >24 hours from admission to participating hospital to consent.
2. Patients admitted to burn unit >24 hours from injury or accident.
3. Patients who are moribund (not expected to survive the next 72 hours).
4. Pregnancy (pregnancy will be ruled out as part of standard of care) or lactating.
5. Enrolment in another industry sponsored ICU interventional study
6. Receiving high-dose IV vitamin C already (enteral or oral vitamin C is allowed).
7. Known glucose-6-phosphate dehydrogenase (G6PD) deficiency.
8. Recent history of kidney stones (within the last year).
9. Concomitant use of hydroxocobalamin (vitamin B12) for suspected cyanide poisoning.

These criteria are designed to include those severe burn injury patients who are likely to benefit from the therapeutic intervention tested in this trial. For the nutrients to have a beneficial effect, particularly on resuscitation outcomes, they have to be delivered as soon after the injury as possible (ideally within 3- 6 hours of admission). However, we acknowledge that it will require some time for research staff to obtain informed consent. We will exclude patients not likely to benefit from the intervention (not likely to survive beyond 72 hours) or those in whom the safety of high dose intravenous vitamin C is uncertain (pregnant patients and patients with G6PD deficiency). High dose vitamin C appears safe in kidney disease except for patients who may have had recent kidney stones or who have received vitamin B12 since it excretes oxalate acid in the kidneys as well. Consistent with other trials of high dose vitamin C, we will recruit patients with kidney injury or failure but exclude patients with recent history of kidney stones.

2.6 What is the proposed duration of treatment period?

96 hours based on [name] trials demonstrating safety and efficacy of this duration. Shorter dosing intervals have demonstrated a reoccurrence of hypovitaminosis after stopping the study intervention.^{25,57}

If a study patient is prematurely withdrawn from the trial (see safety criteria in section 1.5), the timing and reason for the withdrawal from vitamin C administration will be noted and complete study outcomes will continue to be collected. Patients withdrawn from vitamin C/placebo administration will be followed up for 3 days after last administration of the investigational product. If patients withdraw from the entire study, the collected study data will be kept to ensure safety, but no further data will be collected. As we expect this event to be rare, we will not replace such subjects.

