The safety profile for vitamin C in ICU patients is remarkably favourable.⁶⁷ Real-time in the field monitoring of safety events has not revealed any safety issues (personal communication, McGuff Pharmaceuticals, Inc., Department of Regulatory Affairs, Ascor® (Ascorbic Acid Injection, USP) PADER Synopsis, Year 5, NDA 209112). However, there are several complications that may develop which will be closely monitored as ‘Events of Interest’ or outcomes in this trial. One of the potential risks is the formation of calcium oxalate crystals in renal tubule. However, this occurs at much higher doses than those being tested in the VICToRY Trial. Cancer patients, for example, sometimes receive vitamin C doses approximately 40-50 times greater than the dose we are planning to administer albeit over a longer period of time.^{68,69} We will nonetheless monitor acute kidney injury (as an outcome in this trial).

Another potential risk, albeit rare, is factitious hyperglycemia as recorded by capillary blood sugar point-of-care devices as the molecular structure of vitamin C and glucose are similar. This phenomenon does not occur with core lab assays and some point-of-care devices.^{70,71} Accordingly, we are going to mandate that glucose can only be measured with one of the 3 following systems up to 7 days after the last dose of the investigational product (even if patient is transferred on ward) : 1) core lab, 2) point-of-care arterial blood gas machine that has been validated in the setting of high plasma concentrations of vitamin C, 3) Nova Biomedical StatStrip glucometer that has been validated to be accurate in the presence of high concentrations of ascorbic acid. Episodes of true hypoglycemia (<3.8 mmol/L) will be captured in the case report form.

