2.7 What is the proposed duration of follow-up?

Patient clinical status will be monitored daily during the acute care unit stay for up to 3 days after termination of study IP (maximum 7 days). Hospital outcomes will be abstracted from the chart once the patient is discharged.

2.8 and 2.9 What are the proposed primary and secondary outcome measures?

The primary outcome for this phase III trial is persistent organ dysfunction (POD)+death at 28 days, a novel composite endpoint that combines being alive and being free of organ support (inotropes or vasopressors or mechanical circulatory assistance, renal replacement therapy and mechanical ventilation).⁷⁷

The most important secondary endpoint of this trial will be “time to discharge alive from hospital.” The other secondary outcomes will be the components of 28-day POD which include mortality, use of inotropes or vasopressors or mechanical circulatory assistance, renal replacement therapy and mechanical ventilation and POD-free days in the first 28 days.

Tertiary outcomes will include intensive care unit (ICU) outcomes (e.g. length of stay, duration of mechanical ventilation, and readmission rates); hospital outcomes (hospital mortality, length of stay, bacteremia with gram-negative bacilli, and readmission rates); and 6-month outcomes (mortality, health related quality of life and physical function domain of the Short Form-36 (SF-36) questionnaire, activities of daily living and instrumental activities of daily living). We will also record frequency of operative procedures for burn care, presence of inhalation injury, blood transfusions, and other major cost drivers to support our economic evaluation.

2.10 What is the proposed sample size and what is the justification for the assumptions underlying the power calculation?

The primary outcome for this trial is PODS+death at 28 days after randomization. Based on estimates from currently available pooled data from the RE-ENERGIZE study with $\geq 20\%$ TBSA (n=539), we estimate that the 28-day PODS rate will be 27%. Based on our simulations accounting for two interim analyses (see Tables in Appendix C), we estimate that with 333 subjects per arm, we would achieve 78% power to observe a reduction at a one-sided alpha of 0.025 (or two-sided alpha=0.05) if the rate of PODS at 28 days was reduced from 27% to 18% (RRR=33.3%).

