Appendix B: Schedule of Assessments

SCHEDULE OF ASSESSMENTS	Screening / Baseline Day 1	Day 2	Day 3	Day 4	Day 5	Day 6	Day 7	Day 8	Ad Hoc	Outcomes (d/c to 90 days max)	6 Month Follow-Up	Early withdrawal
SCREENING/Pre-RANDOMIZATION (collected once)												
Obtain Consent												
Rule-out Pregnancy (if applicable) as SOC												
Inclusion Criteria met (age; burn size)												
Exclusion Criteria - none present												
BASELINE (collected once at beginning of study period)												
Randomization												
Demographics, Comorbidities, APACHE II Score, hospital & ACU admit date/time												
Burn Injury Assessment (date/time; type; % TBSA)												
Clinical Frailty Scale assessment												
TRAUMA (collected once at baseline)												
Traumatic Brain Injury, GCS, other trauma												
SOFA (record from ACU admission to 3 days after last dose of IP)												
PaO ₂ /FiO ₂ (lowest)												
Platelets (lowest)												
MAP (lowest)												
MICROBIOLOGY (record from >72 hours after ACU admission to ACU discharge for a maximum of 3 months)												
Gram negative bacteremias												
VENTILATION/RRT (record data from hospital admission to hospital discharge for a maximum of 3 months)												
Invasive Mechanical Ventilation												
Renal Replacement Therapy (dialysis)												

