VASOPRESSORS and INOTROPES (record from ACU admission to ACU discharge for a maximum of 3 months)												
Vasopressors/Inotropes (highest hourly rate) for each: dobutamine, dopamine, epinephrine, levosimendan, milrinone, norepinephrine, phenylephrine, vasopressin.												
VITAMIN C DOSING (record all doses received)												

SCHEDULE OF ASSESSMENTS	Screening / Baseline Day 1	Day 2	Day 3	Day 4	Day 5	Day 6	Day 7	Day 8	Ad Hoc	Outcomes (d/c to 90 days max)	6 Month Follow-Up	Early withdrawal
Vitamin C administration (start/stop times; volume infused; interruptions)												
DAILY LABORATORY (record labs ordered as SOC from ACU admission to 3 days after last dose of IP)												
Creatinine, serum (highest)												
Bilirubin, Total (highest)												
Urea (highest)												
Glucose (closest to 8:00 A.M.)												
Hypoglycemic events (record up to 3/day)												

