Severe acid-base imbalance												

SCHEDULE OF ASSESSMENTS	Screening / Baseline Day 1	Day 2	Day 3	Day 4	Day 5	Day 6	Day 7	Day 8	Ad Hoc	Outcomes (d/c to 90 days max)	6 Month Follow-Up	Early withdrawal
Severe electrolyte imbalance												
Refractory hypoglycemia												
SERIOUS ADVERSE EVENTS (recorded within 24 hrs of awareness, from randomization to 3 days after the last dose of IP)												
Event description, seriousness, outcome, expectedness, relationship to IP, action taken with IP, action taken to treat event												
HOSPITAL OVERVIEW (recorded once after hospital discharge to a maximum of 3 months)												
ACU – date of discharge, death, or consent withdrawal.												
Hospital – date of discharge, death, or consent withdrawal.												
Location discharged to or cause of death.												
COVID-19 (collected once and recorded at hospital discharge, or 3 months after admission)												
COVID-19 Status, negative, positive, presumed positive, not tested/unknown and date of result or determination												
SURVIVAL ASSESSMENT (collected once at 6 months after admission (+/- 14 days))												
Alive or deceased, date, source of data.												
If data not obtained, record efforts made, and date last known to be alive.												
HEALTH RELATED QUALITY OF LIFE ASSESSMENTS (collected once at 6 months after admission (+/- 14 days))												
SF-36 questionnaire												
Katz ADL questionnaire												
Lawton IADL questionnaire												
Data Query Resolution (resolve after data entry milestones: hospital overview and survival/6-month assessments)												
Data query checks are built into the EDCS and will generate queries to address missing, inconsistent, and illogical data.												

Data Quality Management and Source Verification/Monitoring

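### SAE, SOFA, daily-laboratory and urine-output recording ends 3 days after the last dose, so patients stopped early are observed for less time, which can bias safety comparisons if stopping differs by arm

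*Combined protocol and SAP*

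**What the plan says.** Section 2.6 has two statements about patients taken off study product early. The first is that "complete study outcomes will continue to be collected". The next is "Patients withdrawn from vitamin C/placebo administration will be followed up for 3 days after last administration of the investigational product". The section does not say which data each statement covers. Section 2.7 sets daily monitoring in the acute care unit "for up to 3 days after termination of study IP (maximum 7 days").

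Appendix B sets a recording window for each block (closing brackets are left off the quoted row titles):

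- "SOFA (record from ACU admission to 3 days after last dose of IP"
- "DAILY LABORATORY (record labs ordered as SOC from ACU admission to 3 days after last dose of IP", a block that contains creatinine, LDH, haptoglobin, arterial pH and hypoglycaemic events
- fluid balance, including urine output, to the same end point
- "SERIOUS ADVERSE EVENTS (recorded within 24 hrs of awareness, from randomization to 3 days after the last dose of IP"

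Other blocks do not depend on the last dose. Ventilation and renal replacement therapy are recorded to hospital discharge and vasopressors to acute-care discharge, each for at most 3 months. Survival is assessed at 6 months. Events of interest that lead to stopping are recorded only between the start and the stop of study product.

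Section 1.5 lets the treating physician stop study product for a new oxalate stone, severe haemolysis, severe acid-base or electrolyte imbalance, refractory hypoglycaemia, or another complication such as an SAE. The same section names acute kidney injury as an outcome to be monitored. It has the Data Monitoring Committee (DMC) review KDIGO rates and renal replacement therapy by group each year, and allows an ad hoc review after two or more similar SAEs.

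**The concern.** A safety comparison between randomised arms needs the same observation time in both, or at least a time that treatment does not influence. Here the end of observation is tied to the last dose, and section 1.5 ties the last dose to the harms under suspicion. A patient stopped on the first day for suspected toxicity leaves SAE, creatinine, SOFA and urine-output recording sooner after randomisation than a patient who tolerated the full course.

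At stake are the comparisons that rest on these blocks: kidney injury that does not reach dialysis, and non-fatal SAEs. Little else captures such events once the product is stopped. Section 2.20 reports no adverse events beyond the pre-specified outcomes and SAEs, and events of interest end when the product stops. The protocol itself cites reports of renal failure with high-dose vitamin C, so creatinine-based ascertainment matters. If more patients stop on vitamin C, the DMC would see counts that lean towards no harm.

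**Working it through.** **1. Reproduce the stated maximum.** Section 2.7 gives 7 days: 96 h of treatment plus 3 days is 96/24 + 3 = 7.0 days. This agrees.

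**2. Window by number of doses received.** Inputs: dosing every 6 h (section 2.2), 16 doses in a full course (section 2.16), recording to last dose + 72 h (Appendix B). With k doses on schedule, days from first dose = ((k − 1) × 6 + 72)/24.

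| Doses received | Last dose (h) | Window (days) | Ratio to completer |
|---|---|---|---|
| 1 | 0 | 3.00 | 0.44 |
| 4 | 18 | 3.75 | 0.56 |
| 8 | 42 | 4.75 | 0.70 |
| 12 | 66 | 5.75 | 0.85 |
| 16 | 90 | 6.75 | 1.00 |

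Time from randomisation to first dose is not given and is left out of every row.

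**3. Effect on the arm comparison.** The documents give no early-stop rate, so the rates here are assumptions. Mean window in an arm = f × w + (1 − f) × 6.75, where f is the proportion stopped and w their window. Example, 10% versus 2% stopped after one dose: 0.10 × 3.0 + 0.90 × 6.75 = 6.375 days against 0.02 × 3.0 + 0.98 × 6.75 = 6.675 days. The ratio is 0.955, so the vitamin C window is 4.5% shorter. Across stops after one to eight doses:

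| Stopped, vitamin C vs placebo (assumed) | Vitamin C mean window shorter by |
|---|---|
| 5% vs 2% | 0.9 to 1.7% |
| 10% vs 2% | 2.4 to 4.5% |
| 20% vs 0% | 5.9 to 11.1% |

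**4. Effect on a recorded relative risk.** Assumptions: constant hazard h per day, risk over t days = 1 − exp(−h × t), and stoppers' last dose at hour 24, so their window is (24 + 72)/24 = 4.0 days.

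- At h = 3% per day, risk is 18.3% over 6.75 days and 11.3% over 4 days. With 15% vs 5% stopping and no true effect: 0.85 × 18.3 + 0.15 × 11.3 = 17.3% against 0.95 × 18.3 + 0.05 × 11.3 = 18.0%, recorded RR 0.96.
- If stoppers have h = 9% per day, their risk is 45.5% over 6.75 days and 30.2% over 4 days. Over the full window the arms have 22.4% and 19.7% (RR 1.14). As recorded they have 20.1% and 18.9% (RR 1.06).
- With 5% vs 2% stopping and the same hazards, the no-effect RR is 0.99, and the 9% case moves from 1.04 to 1.02.

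**5. Do the stated limits fit together?** A final dose made up 24 h late (allowed by section 2.2) falls at hour 114, and (114 + 72)/24 = 7.75 days, beyond the 7-day maximum in section 2.7. Appendix B's daily columns end at Day 8, while its dosing row is open to Day 7, from which last dose + 3 days would be Day 10. The dosing row is a recording column and does not show that doses are given that late, but the three limits need one definition.

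**The case against.** The strongest reply is that the serious consequences are captured whenever the product stops. Renal replacement therapy, ventilation, vasopressor use, death and 28-day status do not depend on the last dose, and the DMC reviews renal replacement therapy as well as KDIGO rates. A reader might infer that delayed harms in early stoppers are missed altogether. The documents do not support that: fatal and dialysis-requiring harm is recorded. Every patient, completer or not, also has the same 3 days after the last dose. This stands, and it limits the point to non-dialysis kidney injury, non-fatal SAEs, SOFA and laboratory values.

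The event that prompts the stop is itself recorded: section 2.6 notes the timing and reason, and Appendix B records related events of interest that end treatment. The illustration in step 4 does not count that signal, so it overstates how much would be hidden. Its stopping rates and hazards are also assumed. The trial's own figures are 100% delivery in 15 pilot patients and an expectation above 90% (sections 2.13 and 2.14). This also stands, and it is why the size is stated as a range.

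The two statements in section 2.6 can be read together, as continued outcomes plus 3 days of daily monitoring. That makes them ambiguous, not proven contradictory.

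Two further inferences are tempting. Section 1.5 restricts glucose measurement to certain systems "up to 7 days after the last dose of the investigational product (even if patient is transferred on ward"), while hypoglycaemic events are recorded for 3 days, so a reader might infer a gap within a declared hypoglycaemia risk period. The restriction is there because some meters give falsely high readings; the section defines no such risk period. Next, the Early withdrawal column is blank for the questionnaires under "HEALTH RELATED QUALITY OF LIFE ASSESSMENTS (collected once at 6 months after admission (+/- 14 days"), so a reader might infer that survivors who stop the product are removed from the quality-of-life comparison. The column is undefined, and section 2.6 promises complete outcomes for these patients. It needs clarifying but does not show removal.

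**Conclusion.** The point holds in limited form. For SAEs, SOFA, daily laboratory values and urine output, observation from first dose runs from 3.0 days (one dose) to 6.75 days (full course). Its length depends on a post-randomisation event that section 1.5 links to suspected harms of vitamin C. Following the plan exactly can therefore give unequal ascertainment of creatinine-based kidney injury and non-fatal SAEs, biased towards no harm if stopping is more frequent on vitamin C.

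The deficit is large for an individual early stopper and small for the arm comparison unless stopping is frequent and unequal: 0.9 to 1.7% of mean window at an assumed 5% versus 2%, and up to 11.1% at an assumed 20% versus 0%. The number of missed events cannot be computed from the documents. The primary outcome and the interim rule based on it are untouched. This should be changed because the remedy is cheap, not because the trial's main conclusion is at risk.

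**What to change.** - Record SAEs, SOFA, standard-of-care daily laboratory values, hypoglycaemic events and urine output from randomisation through Day 8 for every randomised patient, whenever study product stopped. Daily data apply while the patient is in the acute care unit.
- Base between-arm and DMC safety comparisons on that common window. List separately any data collected later because of make-up doses, so that the comparison does not again depend on the last dose.
- Reconcile section 2.6 (complete outcomes versus 3 days), section 2.7 (maximum 7 days) and the Day 8 columns of Appendix B with this window.
- State that patients who stop study product but remain in the study complete all 28-day and 6-month assessments, including SF-36, Katz and Lawton, and that the Early withdrawal column applies to withdrawal from the study only.

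The cost is protocol and case-report-form wording and a few extra days of chart abstraction for early stoppers. No new tests are needed, because the laboratory values are those ordered in routine care. Discharge from the acute care unit before Day 8 would still shorten the daily data, but the window would no longer be set by the date of the last dose.

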2.7 What is the proposed duration of follow-up?

Patient clinical status will be monitored daily during the acute care unit stay for up to 3 days after termination of study IP (maximum 7 days). Hospital outcomes will be abstracted from the chart once the patient is discharged.

2.8 and 2.9 What are the proposed primary and secondary outcome measures?

The primary outcome for this phase III trial is persistent organ dysfunction (POD)+death at 28 days, a novel composite endpoint that combines being alive and being free of organ support (inotropes or vasopressors or mechanical circulatory assistance, renal replacement therapy and mechanical ventilation).⁷⁷

The most important secondary endpoint of this trial will be “time to discharge alive from hospital.” The other secondary outcomes will be the components of 28-day POD which include mortality, use of inotropes or vasopressors or mechanical circulatory assistance, renal replacement therapy and mechanical ventilation and POD-free days in the first 28 days.

Tertiary outcomes will include intensive care unit (ICU) outcomes (e.g. length of stay, duration of mechanical ventilation, and readmission rates); hospital outcomes (hospital mortality, length of stay, bacteremia with gram-negative bacilli, and readmission rates); and 6-month outcomes (mortality, health related quality of life and physical function domain of the Short Form-36 (SF-36) questionnaire, activities of daily living and instrumental activities of daily living). We will also record frequency of operative procedures for burn care, presence of inhalation injury, blood transfusions, and other major cost drivers to support our economic evaluation.

2.10 What is the proposed sample size and what is the justification for the assumptions underlying the power calculation?

The primary outcome for this trial is PODS+death at 28 days after randomization. Based on estimates from currently available pooled data from the RE-ENERGIZE study with $\geq 20\%$ TBSA (n=539), we estimate that the 28-day PODS rate will be 27%. Based on our simulations accounting for two interim analyses (see Tables in Appendix C), we estimate that with 333 subjects per arm, we would achieve 78% power to observe a reduction at a one-sided alpha of 0.025 (or two-sided alpha=0.05) if the rate of PODS at 28 days was reduced from 27% to 18% (RRR=33.3%).

Given the 30-36% relative risk reduction in mortality observed in the meta-analysis reported in section 1.2, we believe this treatment effect to be plausible. The simulated power under various effect sizes accounting for the interim analyses is provided in Appendix C. Based on our several prior studies in this field, we expect to obtain the 28-day PODS status on virtually all patients. Since the randomization is stratified by site and the analysis will control for site, the possible presence of between-site heterogeneity in overall rates will not decrease the power, assuming that the effect of treatment is consistent across sites.

A sample size of 666 patients also provides adequate power for one of our key secondary outcomes, time to discharge from hospital alive. Based on estimates from currently available pooled data from the RE-ENERGIZE study with $\geq 20\%$ TBSA (n=539), we estimate that the median time to hospital discharge is 47 days, by which time no more than 10% would have died. We consider death a competing risk precluding live hospital discharge and, for this outcome, conservatively assume that the intervention has no effect on mortality. With 333 patients per arm followed for up to 182 days and allowing for 5% loss to follow-up, we would achieve 90% power at a two-sided alpha of 0.05 to compare the cumulative incidence of time to alive hospital discharge over 6 months, if the subdistribution hazard ratio of time to live discharge was 1.32. Assuming time to discharge follows an exponential distribution except allowing for the competing risk of death, this effect size would equate to 60% vs. 50% of patients being

discharged alive by day 47 in the intervention and control arm respectively. However, power will decrease due to the interim analysis. The interim analysis will reduce the power by 1% if the RR for PODS+death is 0.667 and the power for time to discharge alive will remain above 80% if the RR of PODS+death is less than 0.85.

We acknowledge that we cannot comment on minimally clinically important differences (MCIDs) in these key endpoints and whether our trial is adequately powered to detect a MCID. This is a problem for all critical-care trials, in which small changes in mortality are important from a patient's perspective; yet detecting such changes would require enrolment of thousands of patients. Rather, we propose a trial that is feasible within the duration of the grant and powered to show a moderate difference in a validated outcome measure. We will be judicious in the interpretation of our results. Thus, if there is a numerical advantage to the study intervention within the range of clinical importance but without statistical significance, our trial results will be "indeterminate".⁷⁸ Fortunately, such trials can be combined statistically with other similar trials, using meta-analysis techniques, to illuminate smaller treatment effects.

2.11 Health service research issues:

Burn care of hospitalized patients is extremely costly, and the cost is related to the severity of the injury.⁷⁹ From the 2013 American Burn Association Repository, the mean hospital charge of burn care was \$US 84,431 per patient (based on 67,115 patients). These charges include patients with minor burns. Patients with burns >20% are much more costly and the charges associated with burn care increase with the severity of burns. Simple interventions, like vitamin C, might result in substantial economic savings from complications averted. If the current trial demonstrates efficacy, we would propose to conduct an economic evaluation using data collected in the phase III trial.

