Once consent is obtained, and necessary baseline data collected for qualifying patients, the study co-ordinator will log on to the web-based randomization system at the Clinical Evaluation Research Unit at Queen's University. The system will confirm eligibility prior to allowing randomization. The system will then provide the study co-ordinator with a patient study number and who will then contact the local pharmacist or delegate with notification of randomization. The unblinded pharmacist or delegate will then access the system to determine the treatment assignment. Allocation will be random and concealed and will be blinded to everyone except the pharmacist at each site who will be responsible for preparing study samples and delivering them to the ICU in a blinded fashion in accordance with the documented study operating procedures. The randomization system, which has proven reliable in several prior RCTs, has a robust audit trail, and will maintain concealment and blinding.

The randomization system will use a computer-generated randomization schedule allocating patients 1:1 to either vitamin C or matching placebo by the method of permuted blocks of random undisclosed size stratified by centre. The study statistician will be responsible for generating the randomization codes and will keep these codes in a password protected file on a private drive on the servers at Kingston Health Science Center. Given the large pragmatic nature of the definitive trial, we will not stratify by additional factors such as burn severity. Since there are no antidotes to Vitamin C, there are no unblinding procedures. Study IP stopping rules are articulated in section 1.5.

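### The 90% power for time to discharge alive does not match 60% vs 50% discharged by day 47 once equal, appreciable mortality is assumed

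*Combined protocol and SAP*

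**What the plan says.** Section 2.10 treats time to discharge alive as a key secondary outcome, with death as a competing risk. It takes a control median of 47 days, with at most 10% dead by then. For this outcome it will "for this outcome, conservatively assume that the intervention has no effect on mortality".

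The power statement first sets out the design: "With 333 patients per arm followed for up to 182 days and allowing for 5% loss to follow-up". The result claimed for that design is that "we would achieve 90% power at a two-sided alpha of 0.05", and the condition attached to the claim is "if the subdistribution hazard ratio of time to live discharge was 1.32". The effect is then translated into proportions discharged alive by day 47, vitamin C against control: "this effect size would equate to 60% vs. 50% of patients being" so discharged. The distribution behind the translation is given as follows: "Assuming time to discharge follows an exponential distribution except allowing for the competing risk of death". On the interim looks, the section adds that "the power for time to discharge alive will remain above 80% if the RR of PODS+death is less than 0.85".

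Section 2.16 specifies a Cox model for the subdistribution hazard with site frailty and baseline covariates. Patients who die before discharge are given censoring times beyond the end of follow-up, so they stay in the risk set throughout, as in a Fine and Gray analysis.

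**The concern.** With deaths kept at risk, the discharge curve in each arm can rise no higher than one minus the share who die in hospital. If mortality is the same in both arms, the curves separate early and close up later. The sHR therefore starts above 1, declines, and can fall below 1 late in follow-up.

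The value 1.32 is the ratio implied by the two day-47 percentages. Using it as the effect over all 182 days assumes that the early separation persists. With a 47-day median, few survivors are still in hospital at six months, so it cannot persist unless mortality differs or is very low.

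Section 2.8 and 2.9 ranks this as the leading secondary outcome. If 90% is overstated for the effect the reader is shown, a non-significant result would look more informative than it is.

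**Working it through.** **Inputs.** From section 2.10: 333 per arm, 182 days, 5% loss, two-sided alpha 0.05, sHR 1.32, 60% vs 50% at day 47, at most 10% dead by day 47, no mortality effect. From section 2.3: "allocating patients 1:1 to either vitamin C or matching placebo". From section 2.16: deaths stay in the risk set. The 5% and 2.5% mortality values are assumptions.

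**1. Source of 1.32.** ln(0.4)/ln(0.5) = 1.322, the exponential translation of 60% vs 50% at day 47.

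**2. Reproducing 90%.** Hold the sHR at 1.32 throughout.
- Exponential curves at day 182: control 1 − 0.5^(182/47) = 93.2%; vitamin C 1 − 0.0683^1.32 = 97.1%; mean 95.1%.
- Events, deducting 5% loss and 10% deaths in both arms: 666 × 0.95 × 0.90 × 0.951 = 542.
- Power = Φ(½ × √542 × ln 1.32 − 1.96) = Φ(3.23 − 1.96) = 89.8%.
- Without the death deduction: 602 events, 92.6%.

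The stated 90% is reproduced. The protocol does not say which route it took, so the 10% deduction is a reconstruction.

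**3. What a constant 1.32 implies for mortality.** If the control curve levels off at 90%, the vitamin C curve levels off at 1 − 0.10^1.32 = 95.2%. Deaths would be 10% vs 4.8%, which is not equal mortality.

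**4. Equal mortality, with 60% vs 50% kept.** Suppose a share m dies in each arm and survivors' discharge is exponential: F(t) = (1 − m)(1 − e^(−λt)). With m = 0.10:
- λ(control) = −ln(1 − 0.5/0.9)/47 = 0.01725; λ(vitamin C) = −ln(1 − 0.6/0.9)/47 = 0.02337; rate ratio 1.355.
- Discharged alive by day 182: 86.1% vs 88.7%.
- Ratio of cumulative subdistribution hazards at day 182: ln(0.113)/ln(0.139) = 2.18/1.97 = 1.11, against 1.32 at day 47.
- Instantaneous sHR: 1.35 at day 1, 1.27 at day 47, 1.08 at day 90, 0.90 at day 120, 0.55 at day 182.

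**5. Simulated power.** 333 per arm, 5% lost uniformly over 182 days, unadjusted subdistribution Cox Wald test. Two readings of no mortality effect were used: the same share dying in each arm (the percentage is the total share), or the same death hazard in each arm (the percentage is control deaths by day 47).

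| Deaths | Average sHR over 182 days | Power |
|---|---|---|
| 10% | 1.22–1.26 | 67–76% |
| 5% | 1.26–1.28 | 80–84% |
| 2.5% | 1.29–1.30 | 87–88% |

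The equal-share reading gives the lower end at 10% and 5%; at 2.5% the two nearly coincide. Repeat runs agree within about two points. Removing the 5% lost at the outset instead gives 64–75% at 10% and 80–81% at 5%. A constant sHR of 1.32 with no deaths deducted gives 93–94%.

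**6. Reverse check.** Under equal shares dying, an average sHR near 1.32 is recovered at 64% vs 50% by day 47 with 10% deaths (sHR 1.32, power 92%), and at 62% vs 50% with 5% deaths (sHR 1.31, power 91.5%).

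**The case against.** The strongest reply is that the 90% is conditional on the sHR, and 60% vs 50% is only a gloss on it. This stands. The arithmetic is correct on its condition, and step 6 shows that an average sHR of 1.32 gives about 90% power or more under equal mortality. The fault lies in pairing that sHR with 60% vs 50%, so correcting the translation is as valid a repair as restating the power.

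Second, 10% is an upper bound, not an estimate. This also stands: at 2.5% deaths the loss is only two or three points. Third, assuming no mortality benefit is conservative in direction, because it lowers power for this outcome; the problem is that the 90% does not reflect it. Fourth, the simulations leave out site frailty and covariate adjustment, so the figures are approximate.

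A constant sHR with equal mortality is possible in principle if many patients remain in hospital at day 182. The stated exponential with a 47-day median rules that out.

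A reader might infer three stronger things:
- **That the trial is underpowered for this outcome.** The range straddles 80%, and the documents do not fix mortality within it.
- **That the above-80% sentence is false.** No calculation here included stopping. Appendix C, Table B has 10.0 + 1.0 = 11.0% of trials stopping early at RR 0.8 and 20.5 + 3.4 = 23.9% at RR 0.9. The effect on this outcome depends on how stopping and discharge are correlated, so the sentence is unverified rather than refuted.
- **That a day-90 horizon is the remedy.** It would change the estimand. It raises power from 67–76% to 81–82% at 10% deaths, but moves it from 87–88% to 86–87% at 2.5%.

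**Conclusion.** The point holds as an inconsistency among stated assumptions. An sHR of 1.32 over 182 days, exponential discharge with 60% vs 50% at day 47, equal mortality and deaths near the 10% bound cannot all be true. For the contrast shown to the reader, the overstatement is about 14 to 23 points at 10% deaths (90 − 76 and 90 − 67), 6 to 10 at 5% (90 − 84 and 90 − 80), and 2 to 3 at 2.5% (90 − 88 and 90 − 87). These figures rest on the two mortality models, an unadjusted test and no interim stopping.

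The outcome is secondary. The power for the primary outcome and the 666-patient sample size do not depend on it.

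**What to change.** In section 2.10:
- State the in-hospital mortality assumed for this outcome, and whether no mortality effect means equal shares dying or equal death hazards.
- Then do one of two things. Either restate power for 60% vs 50% at day 47 under equal mortality (about 67–76%, 80–84% and 87–88% at 10%, 5% and 2.5% deaths), or keep 90% for an average sHR of 1.32 and change the translation to about 62 to 64% vs 50%, depending on the mortality assumed.
- Recompute the above-80% statement under the same assumptions with the stopping rule simulated.

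The cost is a few lines of text and one simulation, with possibly a less favourable stated power. No patients are added and the analysis is unchanged. Separately, the 182/183-day horizon in sections 2.10 and 2.16 should be reconciled with the three-month limit on recording hospital discharge in Appendix B; that is not part of this correction.
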